**Table 2. List of Primary, Secondary, CCI Objectives, Endpoints, and Estimands**

 
To demonstrate that the percentages of participants with predefined serotype-specific IgG concentrations for the 7 additional serotypes in the 20vPnC group are noninferior to the lowest percentage among the 13 serotypes in the 13vPnC group at 1 month after Dose 3
 
	
In evaluable participants at 1 month after Dose 3:
 
 
For each of the 7 additional serotypes in 20vPnC: difference in the percentages of participants with predefined serotype-specific IgG concentrations, between the 20vPnC group and the lowest percentage of participants with predefined serotype-specific IgG concentrations among the 13 serotypes from the 13vPnC group
 
	
 
Pneumococcal serotype-specific IgG concentration
 

 
To demonstrate that the serotype-specific IgG GMCs for the 13 serotypes in the 20vPnC group are noninferior to the GMCs for the corresponding serotypes in the 13vPnC group at 1 month after Dose 4
 
	
In evaluable participants at 1 month after Dose 4:
 
 
For each of the 13 matched serotypes: GMR of serotype-specific IgG concentrations from the 20vPnC group to the 13vPnC group
 
	
 
Pneumococcal serotype-specific IgG concentration
 

 
To demonstrate that the serotype-specific IgG GMCs for the 7 additional serotypes in the 20vPnC group are noninferior to the lowest IgG GMC among the 13 serotypes in the 13vPnC group at 1 month after Dose 4
 
	
In evaluable participants at 1 month after Dose 4:
 
 
For each of the 7 additional serotypes in 20vPnC: GMR of serotype-specific IgG concentration from the 20vPnC group to that from the serotype with the lowest IgG GMC among the 13 serotypes from the 13vPnC group
 
	
 
Pneumococcal serotype-specific IgG concentration
 

Primary Concomitant Immunogenicity Objective	Estimand	Primary Concomitant Immunogenicity Endpoints

 
To demonstrate that percentages of participants with prespecified antibody levels to specific concomitant vaccine antigens when given with 20vPnC are noninferior to the corresponding percentages when the antigens are given with 13vPnC at 1 month after Dose 3
 
	
In evaluable participants who receive the appropriate concomitant vaccines:
 
 
Differences in percentages of participants with prespecified antibody levels to diphtheria toxoid, tetanus toxoid, pertussis antigens (PT, FHA, PRN), HBsAg, poliovirus strains, and Hib between the 20vPnC group and the 13vPnC group at 1 month after Dose 3
 
	
 
Antibody levels to diphtheria toxoid, tetanus toxoid, and pertussis antigens (PT, FHA, PRN)
 
Antibody levels to HBsAg
 
Antibody levels to poliovirus strains (types 1, 2, and 3)
 
Antibody levels to Hib
 

**Table 2. List of Primary, Secondary, CCI Objectives, Endpoints, and Estimands**

Key Secondary Pneumococcal Immunogenicity Objectives	Estimands	Key Secondary Pneumococcal Immunogenicity Endpoints

 
To demonstrate that the serotype-specific IgG GMCs for the 13 serotypes in the 20vPnC group are noninferior to the GMCs for the corresponding serotypes in the 13vPnC group at 1 month after Dose 3
 
	
In evaluable participants at 1 month after Dose 3:
 
 
For each of the 13 matched serotypes: GMR of serotype-specific IgG concentrations from the 20vPnC group to the 13vPnC group
 
	
 
Pneumococcal serotype-specific IgG concentration
 

 
To demonstrate that the serotype-specific IgG GMCs for the 7 additional serotypes in the 20vPnC group are noninferior to the lowest IgG GMC among the 13 serotypes in the 13vPnC group at 1 month after Dose 3
 
	
In evaluable participants at 1 month after Dose 3:
 
 
For each of the 7 additional serotypes in 20vPnC: GMR of serotype-specific IgG concentration from the 20vPnC group to that from the serotype with the lowest IgG GMC among the 13 serotypes from the 13vPnC group
 
	
 
Pneumococcal serotype-specific IgG concentration
 

Secondary Pneumococcal Immunogenicity Objective	Estimands	Secondary Pneumococcal Immunogenicity Endpoints

 
To further describe the immunogenicity of 20vPnC
 
	
In evaluable participants at 1 month after Dose 3 and 1 month after Dose 4:
 
 
Serotype-specific OPA GMTs at 1 month after Dose 3, prior to Dose 4, and 1 month after Dose 4 in each group
 
 
In evaluable participants at 1 month after Dose 4:
 
 
For each of the serotypes in 20vPnC: percentages of participants with the predefined serotype-specific IgG concentration in each group
 
 
In evaluable participants:
 
 
GMFRs in serotype-specific IgG concentrations from 1 month after Dose 3 to before Dose 4, from before Dose 4 to 1 month after Dose 4, and from 1 month after Dose 3 to 1 month after Dose 4 in each group
 
	
 
Pneumococcal serotype-specific OPA titers
 
Pneumococcal serotype-specific IgG concentrations
 

**Table 2. List of Primary, Secondary, CCI [REDACTED] Objectives, Endpoints, and Estimands**

Secondary Concomitant Immunogenicity Objectives	Estimands	Secondary Concomitant Immunogenicity Endpoints

 
To further describe the immune responses induced by specific concomitant vaccine antigens given with 20vPnC or 13vPnC
 
To demonstrate that GMCs to specific concomitant vaccine antigens when given with 20vPnC are noninferior to the corresponding GMCs when the antigens given with 13vPnC at 1 month after Dose 4
 
	
In evaluable participants who receive the appropriate concomitant vaccines:
 
 
Differences in percentages of participants with alternative prespecified antibody levels to Hib between the 20vPnC group and the 13vPnC group at 1 month after Dose 3
 
GMRs of antibody levels to measles, mumps, rubella, and varicella viruses from the 20vPnC group to the 13vPnC group at 1 month after Dose 4
 
	
 
Antibody levels to Hib
 
Antibody levels to measles, mumps, rubella, and varicella viruses
 

CCI [REDACTED]
	
[REDACTED]
	
[REDACTED]

[REDACTED]
	
[REDACTED]
	
 
CCI [REDACTED]
 

**Table 2. List of Primary, Secondary, CCI [REDACTED] Objectives, Endpoints, and Estimands**

	

• CCI [REDACTED]

• CCI [REDACTED]

	

• CCI [REDACTED]

CCI [REDACTED]	[REDACTED]	[REDACTED]
[REDACTED]	[REDACTED]	[REDACTED]

## 2.2. Study Design

This Phase 3, multicenter, randomized, double-blind study will be conducted at investigator sites in the United States and Puerto Rico.

Approximately 2000 infants  $\geq 42$  to  $\leq 98$  days of age at the time of consent, by their parent(s)/legal guardian(s), will be enrolled. Participants will be randomized in a 1:1 ratio to receive either 20vPnC or 13vPnC (control vaccine) at 2, 4, 6, and 12 to 15 months of age (Doses 1, 2, 3, and 4, respectively) by site-based randomization. Participants will receive the same vaccine (20vPnC or 13vPnC) for all 4 doses. Specific concomitant vaccines containing diphtheria, tetanus, acellular pertussis, hepatitis B virus, poliovirus, and Hib antigens will also be administered at 2, 4, and 6 months of age and containing measles, mumps, rubella, and varicella antigens at 12 to 15 months of age, respectively.

Blood will be collected 1 month after Dose 3 (7 months of age), immediately prior to Dose 4 (12-15 months of age), and 1 month after Dose 4 (13-16 months of age) to assess immunogenicity. Participants will be observed for 30 minutes after each vaccination and any reactions occurring during that time will be recorded as AEs. Prompted local reactions (redness, swelling, and pain at the 20vPnC or 13vPnC injection site), systemic events (fever, decreased appetite, drowsiness/increased sleep, and irritability), and use of antipyretic/pain medications occurring within 7 days after each vaccination will be collected via a provided e-diary (or e-diary application). AEs, including nonserious AEs, will be collected from the signing of informed consent to 1 month after Dose 3 and from Dose 4 to 1 month after Dose 4. SAEs and NDCMCs will be collected for the entire duration of the study.

## 3. ENDPOINTS AND BASELINE VARIABLES: DEFINITIONS AND CONVENTIONS

### 3.1. Primary Endpoints

#### 3.1.1. Primary Safety Endpoints

- Prompted local reactions (redness, swelling, and pain at the injection site) within 7 days after each dose
- Prompted systemic events (fever, decreased appetite, drowsiness/increased sleep, and irritability) within 7 days after each dose
- AEs from Dose 1 to 1 month after Dose 3 and from Dose 4 to 1 month after Dose 4
- SAEs during the study (from Dose 1 to 6 months after Dose 4)
- NDCMCs during the study (from Dose 1 to 6 months after Dose 4)

### 3.1.1.1. Local Reactions

The local reactions assessed and reported in the e-diary are redness, swelling, and pain at the 20vPnC or 13vPnC injection site, from Day 1 through Day 7 after each dose, where Day 1 is the day of each dose. This section describes derivations with details for the assessment of local reactions: severity level, duration, and onset day.

#### Severity and Maximum Severity

Redness and swelling will be measured and recorded in measuring device (caliper) units, and then categorized during analysis as mild, moderate, or severe based on the grading scale in Table 3. Grade 4 will not be collected in the e-diary but will be collected as an AE on the CRF. Measuring device units can be converted to centimeters according to the following scale: 1 measuring device unit = 0.5 cm. Pain at the vaccine injection site will be assessed by the participant’s parent(s)/legal guardian(s) as mild, moderate, or severe according to the grading scale in Table 3.

**Table 3. Grading Scales for Local Reactions**

Local Reaction	GRADE 1 Mild	GRADE 2 Moderate	GRADE 3 a Severe	GRADE 4 b
Redness	1 to 4 caliper units (or measuring device units) = >0 to 2.0 cm	5 to 14 caliper units (or measuring device units) = >2.0 to 7.0 cm	>14 caliper units (or measuring device units) = >7.0 cm	Necrosis or exfoliative dermatitis
Swelling	1 to 4 caliper units (or measuring device units) = >0 to 2.0 cm	5 to 14 caliper units (or measuring device units) = >2.0 to 7.0 cm	>14 caliper units (or measuring device units) = >7.0 cm	Necrosis
Pain at injection site	Hurts if gently touched (eg, whimpers, winces, protests, or withdraws)	Hurts if gently touched with crying	Causes limitation of limb movement	Emergency room visit or hospitalization for severe pain (tenderness) at injection site

Abbreviation: CRF = case report form.

**Note:** If the size of the redness and/or swelling falls between 2 measuring device units, the higher measuring device unit number will be recorded in the e-diary.

- a. Parents/legal guardians of the participants experiencing local reactions >14 caliper units (>7.0 cm) are to be contacted by the study site. An unscheduled visit may be required.
- b. Grade 4 assessment should be made by the investigator. Grade 4 will not be collected in the e-diary but will be collected as an AE on the CRF.

For each local reaction after each dose, the maximum severity grade will be derived for the e-diary collection period (Day 1 through Day 7, where Day 1 is the day of each dose) as follows:

maximum severity grade = highest grade (maximum severity) within 7 days after vaccination (Day 1 through Day 7) among severity grades reported for that local reaction in the e-diary.

CCI [REDACTED]

[REDACTED]

[REDACTED]

[REDACTED]

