8.2.1. Participant Electronic Diary

The participant's parent(s)/legal guardian(s) will be asked to monitor and record local reactions, specific systemic events, and antipyretic/pain medication taken for 7 days, each evening, following each study vaccination using an e-diary (in a provisioned device or application on a personal device). This allows recording of these assessments only within a fixed time window, thus providing the accurate representation of the participant's experience. Data on local reactions, specific systemic events, and antipyretic/pain medication reported in the e-diary will be transferred electronically to the e-diary vendor, where they will be available for review by investigators, their qualified designees, and sponsor staff at all times via an internet-based portal. At intervals agreed to by the vendor and Pfizer, these data will be transferred electronically to Pfizer for analysis and reporting.

The daily e-diary data will not be captured in the CRF. However, if a participant is withdrawn because of prompted events reported in the e-diary, the event(s) should be recorded on the AE page of the CRF, regardless of whether the investigator considers the event(s) to be clinically significant.

The investigator or designee must obtain stop dates for any local reactions or specific systemic events on the last day that the e-diary was completed. The stop dates should be entered in the CRF.

Investigators (or an appropriately qualified designee) are required to review the e-diary data online at frequent intervals (daily is optimal) to evaluate participant compliance and reported events as part of the ongoing safety review.

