10.3.3. Definition of SAE

If an event is not an AE per definition above, then it cannot be an SAE even if serious conditions are met (eg, hospitalization for signs/symptoms of the disease under study, death due to progression of disease).

An SAE is defined as any untoward medical occurrence that, at any dose:

a. Results in death

b. Is life-threatening

The term "life-threatening" in the definition of "serious" refers to an event in which the participant was at risk of death at the time of the event. It does not refer to an event that hypothetically might have caused death if it were more severe.

c. Requires inpatient hospitalization or prolongation of existing hospitalization

In general, hospitalization signifies that the participant has been detained (usually involving at least an overnight stay) at the hospital or emergency ward for observation and/or treatment that would not have been appropriate in the physician's office or outpatient setting. Complications that occur during hospitalization are AEs. If a complication prolongs hospitalization or fulfills any other serious criteria, the event is serious. When in doubt as to whether "hospitalization" occurred or was necessary, the AE should be considered serious.

Hospitalization for elective treatment of a preexisting condition that did not worsen from baseline is not considered an AE.

d. Results in persistent disability/incapacity

- The term disability means a substantial disruption of a person's ability to conduct normal life functions.
- This definition is not intended to include experiences of relatively minor medical significance such as uncomplicated headache, nausea, vomiting, diarrhea, influenza, and accidental trauma (eg, sprained ankle) which may interfere with or prevent everyday life functions but do not constitute a substantial disruption.

e. Is a congenital anomaly/birth defect

f. Other situations:

- Medical or scientific judgment should be exercised in deciding whether SAE reporting is appropriate in other situations such as important medical events that may not be immediately life-threatening or result in death or hospitalization but may jeopardize the participant or may require medical or surgical intervention to prevent one of the other outcomes listed in the above definition. These events should usually be considered serious.

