- Mild: An event that is easily tolerated by the participant, causing minimal discomfort and not interfering with everyday activities.
- Moderate: An event that causes sufficient discomfort and interferes with normal everyday activities.
- Severe: An event that prevents normal everyday activities. An AE that is assessed as severe should not be confused with an SAE. Severe is a category utilized for rating the intensity of an event; and both AEs and SAEs can be assessed as severe.

An event is defined as “serious” when it meets at least 1 of the predefined outcomes as described in the definition of an SAE, NOT when it is rated as severe.

GRAD E	If required on the AE page of the CRF, the investigator will use the adjectives MILD, MODERATE, or SEVERE to describe the maximum intensity of the AE. For purposes of consistency, these intensity grades are defined as follows:	
1	MILD	Does not interfere with participant's usual function.
2	MODERATE	Interferes to some extent with participant's usual function.
3	SEVERE	Interferes significantly with participant's usual function.

Assessment of Causality

- The investigator is obligated to assess the relationship between study intervention and each occurrence of each AE/SAE.
- A “reasonable possibility” of a relationship conveys that there are facts, evidence, and/or arguments to suggest a causal relationship, rather than a relationship cannot be ruled out.
- The investigator will use clinical judgment to determine the relationship.
- Alternative causes, such as underlying disease(s), concomitant therapy, and other risk factors, as well as the temporal relationship of the event to study intervention administration will be considered and investigated.
- The investigator will also consult the IB and/or product information, for marketed products, in his/her assessment.
- For each AE/SAE, the investigator **must** document in the medical notes that he/she has reviewed the AE/SAE and has provided an assessment of causality.
- There may be situations in which an SAE has occurred and the investigator has minimal information to include in the initial report to the sponsor. However, **it is very important that the investigator always make an assessment of causality for every event before the initial transmission of the SAE data to the sponsor.**
- The investigator may change his/her opinion of causality in light of follow-up information and send an SAE follow-up report with the updated causality assessment.

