### 3.1.1.2. Systemic Events (Systemic Event Symptoms and Fever)

The systemic events assessed and recorded in the e-diary are fever, decreased appetite, drowsiness/increased sleep, and irritability from Day 1 through Day 7, where Day 1 is the day of each dose. The derivations for systemic events will be handled similarly to the way local reactions are handled for severity level, duration, and onset day (see [Section 3.1.1.1](#)). Maximum temperature range over the period from Day 1 through Day 7 will be mapped into the ranges described in [Table 5](#) for summary of maximum temperature.

The systemic events of decreased appetite, irritability, and drowsiness/increased sleep will be assessed by participants parents/legal guardians as mild, moderate, or severe according to the grading scale in [Table 4](#). Grade 4 will not be collected in the e-diary but will be collected as an AE on the CRF.

[REDACTED]

[REDACTED]

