**3.1.1.4. Adverse Events**

AEs will be categorized according to MedDRA terms. AEs will be assessed from the time of informed consent through 1 month after Dose 3 and from Dose 4 through 1 month after Dose 4.

[REDACTED]

[REDACTED]

The primary endpoint “AEs from Dose 1 through 1 month after Dose 3 and from Dose 4 through 1 month after Dose 4” and other supportive AE endpoints will be summarized by system organ class and preferred term on a participant level.

This primary endpoint will be supported by summaries and listings of related AEs, severe AEs, and immediate AEs (within the first 30 minutes after each dose).

AE reporting will be based on the specific reporting period. Missing AE start dates will be imputed following the Pfizer data standard rules as described in [Section 5.3](#).

A 3-tier approach will be used to summarize AEs from Dose 1 through 1 month after Dose 3 and, separately, from Dose 4 through 1 month after Dose 4. Under this approach, AEs are classified into 1 of 3 tiers. Different analyses will be performed for different tiers (see [Section 6.1.1.3.1](#)).

- Tier 1 events: These are prespecified events of clinical importance and are identified in a list in the product’s safety review plan. No Tier 1 events have been identified to date for 20vPnC.
- Tier 2 events: These are events that are not Tier 1, but are “relatively common.” A MedDRA preferred term is defined as a Tier 2 event if there are at least 1% participants with the AE term in at least 1 vaccine group.
- Tier 3 events: These are events that are neither Tier 1 nor Tier 2.

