### 6.1.1.3. Adverse Events

#### 6.1.1.3.1. Main Analysis

- Estimands:
  - The percentages of participants reporting AEs from Dose 1 to 1 month after Dose 3 ([Section 2.1](#)).
  - The percentages of participants reporting AEs from Dose 4 to 1 month after Dose 4 ([Section 2.1](#)).
- Analysis set: Safety population ([Section 4](#)).
- Analysis time points: Dose 1 to 1 month after Dose 3 and Dose 4 to 1 month after Dose 4.
- Analysis methodology: 3-Tiered approach as described in [Section 5.2.1](#).

[REDACTED]

[REDACTED]

- Intercurrent events and missing data: No missing values will be imputed except for partial AE start dates ([Section 5.3](#)).
- Reporting results: For all 3 tiers, the numerator (n) and the denominator (N) used in the percentage calculation, the percentage (%), and the corresponding 2-sided 95% CI for participants reporting any AE, by each system organ class and each preferred term within system organ class, will be presented by vaccine group.

In addition, for AEs classified as Tier 2 events, the differences in percentages (20vPnC – 13vPnC) and associated 2-sided 95% CIs will be provided.

Further, for Tier 1 events, if any are identified, the difference in percentages, the associated 2-sided 95% CI for the risk difference, and the asymptotic p-values will also be provided.

CCI [REDACTED]

[REDACTED]

[REDACTED]

CCI [REDACTED]

[REDACTED]

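### Should the by-dose severity tables for prompted reactions include the Grade 4 events that the investigator records as adverse events?

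*SAP*

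**What the plan says.** SAP Tables 3 and 4 define four grades for six prompted symptoms: redness, swelling, injection-site pain, decreased appetite, drowsiness and irritability. Fever is shown by temperature range and has no Grade 4. For redness and swelling, Grades 1 to 3 follow diameter alone. Grade 4 is a tissue change: necrosis for swelling, and necrosis or exfoliative dermatitis for redness. For the other four symptoms, Grade 4 is an emergency room visit or hospitalization for a severe event.

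Grade 4 has a separate route. SAP Section 3.1.1.1 states "Grade 4 will not be collected in the e-diary but will be collected as an AE on the CRF", and the same statement is in Section 3.1.1.2 and in the footnotes to both tables. The maximum grade over Days 1 to 7 is then the highest "among severity grades reported for that local reaction in the e-diary". For systemic symptoms, "The derivations for systemic events will be handled similarly to the way local reactions are handled for severity level".

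On the AE side, Protocol Section 10.3.4 says that "the investigator will use the adjectives MILD, MODERATE, or SEVERE to describe the maximum intensity of the AE", so that scale has three levels. SAP Section 3.1.1.4 adds "summaries and listings of related AEs, severe AEs, and immediate AEs". The main AE analysis in SAP Section 6.1.1.3.1 uses two windows: "Analysis time points: Dose 1 to 1 month after Dose 3 and Dose 4 to 1 month after Dose 4".

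**The concern.** The grading tables define a Grade 4, yet the derivation that feeds the main reactogenicity display cannot return one. Someone who reads only the by-dose severity table could not tell whether no Grade 4 event occurred or whether such events are tabulated elsewhere.

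For pain and the three systemic symptoms the loss is usually one step, because Grade 4 presupposes an event that is already severe. For redness and swelling it can be larger. The parent grades by size, so a confirmed necrosis of small diameter would appear as mild or moderate. If the parent entered no redness or swelling but did enter other diary data, it would appear as no reaction.

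The AE tables do not fully replace the missing row:

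- The CRF intensity scale rates interference with usual function, so a small necrosis need not be rated severe and need not enter the severe-AE summaries.
- An emergency room visit need not be a serious event, because Protocol Section 10.3.3 describes hospitalization in general as a participant who "has been detained (usually involving at least an overnight stay) at the hospital or emergency ward".
- The first AE window pools Doses 1 to 3.

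At stake is the accuracy of a descriptive safety display for a primary objective.

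**Working it through.** The documents give no figure to reproduce here. The check is to trace the rule, then look for where the event is reported.

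**1. The rule applied to a confirmed necrosis.** One measuring device unit is 0.5 cm (SAP Section 3.1.1.1), so 4 units × 0.5 = 2.0 cm and 14 units × 0.5 = 7.0 cm. Both agree with Table 3.

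| E-diary entry for redness or swelling | Derived maximum | Steps below Grade 4 |
|---|---|---|
| None, with other diary data after that dose | No reaction | 4 |
| 1 to 4 units (up to 2.0 cm) | Grade 1 | 3 |
| 5 to 14 units (up to 7.0 cm) | Grade 2 | 2 |
| More than 14 units, entered as 15 | Grade 3 | 1 |

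With no diary data at all after that dose, the participant leaves the denominator (SAP Section 6.1.1.1.1). The highest attainable grade is 3, so the factual part of the concern is correct on the readable text.

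**2. Where the event is reported.** The two data streams are kept apart in both directions: Protocol Section 8.2.1 says "The daily e-diary data will not be captured in the CRF", and Grade 4 does not enter the diary. SAP Section 6.1.1.3.1 reports AEs in all three tiers with n, N, percentage and 95% CI, by system organ class and preferred term, for each vaccine group. Protocol Section 10.3.4 asks for a diagnosis as the AE term where possible. A necrosis would therefore be identifiable by name and by group. This covers the one case in which the diary grade is more than about one step too low. Protocol Sections 8.2.2.1 and 8.2.2.2 also require the investigator to notify the sponsor at once of any Grade 4 event.

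**3. What is not reported.** The AE outputs carry no Grade 4 label. An event after Dose 1, 2 or 3 falls in one pooled window, while an event after Dose 4 has its own.

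**4. Size of one event.** The estimand is the percentage of participants reporting each reaction (SAP Table 2), whatever its grade. The Clopper-Pearson limits are Beta⁻¹(0.025; x, n−x+1) and Beta⁻¹(0.975; x+1, n−x). The first n is 2000/2 = 1000 per group. The second, 800, is an assumed lower figure for participants with diary data.

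| n per group | x = 0 | x = 1 |
|---|---|---|
| 1000 | 0% (0 to 0.368%) | 0.100% (0.0025% to 0.556%) |
| 800 | 0% (0 to 0.460%) | 0.125% (0.0032% to 0.695%) |

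The event counts are illustrative, because the documents give no Grade 4 rate. For one event, the zero shown and the merged value differ by 0.10 to 0.125 percentage points.

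**5. What merging would do.** Taking the higher of the diary grade and the CRF Grade 4 would put two raters in one variable and show the same event in both the reactogenicity and the AE tables. It would also draw the numerator partly from the CRF while the denominator stays with participants who have diary data. A necrosis with no redness or swelling entry would add one to the any-grade count, so the merge could alter the estimated percentage itself.

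**The case for a change.** The best case for a change is this. The protocol grades prompted events on a four-level scale, gives Grade 4 to the investigator alone and requires immediate notice to the sponsor, so the sponsor plainly regards it as important. A severity table that cannot show it does not carry that scale through. The data already exist in the CRF AEs and the sponsor notifications, and a footnote with one listing would cost almost nothing.

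Part of this stands. No readable output shows Grade 4 by vaccine group and dose, and such a listing would help anyone reading the severity tables alone. It does not make the derivation wrong. Redness and swelling are classified in analysis as mild, moderate or severe (SAP Section 3.1.1.1), and a 2 cm redness is correctly mild on a diameter scale. The necrosis is a different observation, made by a different person and reported in the AE tables. The explanation a reader needs is already in the footnotes to SAP Tables 3 and 4.

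Nor can the listing be called absent. Text is redacted directly after the maximum-severity rule, in SAP Section 3.1.1.2, and within the reactogenicity analyses in Section 6.1.1, where a Grade 4 rule or listing would be expected.

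**Conclusion.** No change to the plan is needed. On the readable text the by-dose severity tables contain diary data only and end at Grade 3, because Grade 4 reactions are collected and summarised as AEs by design. Keeping the sources separate is a fair choice, and merging them has drawbacks of its own on which statisticians may reasonably differ.

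The cost is limited to a label and, within Doses 1 to 3, attribution to a dose. One event in a group of 800 to 1000 moves a percentage by 0.125 to 0.10 points. The planned analysis leaves the estimand, the noninferiority tests and the overall safety conclusion unaffected.

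This rests on two assumptions: that Grade 4 events are recorded as AEs under a recognisable term, as the protocol directs, and that they are few, which the documents neither state nor contradict. If the redacted text does not already cover it, the sponsor could footnote the severity tables as diary-only and point to a listing of confirmed Grade 4 events by group and dose. That is a matter of presentation and alters no result.
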